3.2 Registration/Randomization to Step 2 - Arms A, B, C, and D

Rev. 6/14

- \_\_\_\_\_ 3.2.1 Histopathologic assessment of surgical pathology must include examination for perineural invasion (PNI) and lymphovascular invasion (LVI) and reported as absent or present. The absence or presence of extracapsular extension (ECE) requires gross and microscopic assessment and is defined to be:
- absent (negative or nodal metastasis with smooth/rounded leading edge confined to thickened capsule/pseudocapsule),
  - present - minimal (tumor extends  $\leq$  1 mm beyond the lymph node capsule), or
  - present - extensive (Gross, tumor extends  $>$ 1 mm beyond the lymph node capsule (includes soft tissue metastasis)

Rev. 2/15  
Rev. 1/16

- \_\_\_\_\_ 3.2.2 Patient must be stratified/classified into one of the following risk categories:
- The highest risk feature assessed pathologically will determine the patient's category/treatment arm assignment.
- Low Risk: T1-T2, N0-N1 AND clear ( $\geq$  3mm) margins, AND no ECE or PNI/LVI.
  - High Risk: Any of the following features: one or more positive margin(s) with any T stage, OR "Extensive" ( $>$  1mm) ECE, OR  $\geq$  5 metastatic lymph nodes (regardless of primary tumor margin status).
  - Intermediate Risk: Any of the following features: one or more "close" ( $<$  3mm) margin(s), OR "Minimal" ( $\leq$  1mm) ECE, OR N2a (1 or more lymph node  $>$  3cm in diameter), OR N2b (2-4 lymph nodes positive, any diameter  $\leq$  6cm), OR with perineural invasion or lymphovascular invasion.
  - Unknown Risk: Patients found to have N2C or N3 disease on final pathologic analysis are at unknown risk for recurrence, but are not candidates for deintensified adjuvant therapy in this trial. These patients will be treated on Arm C.
  - **Patients not categorized into the appropriate risk category will be considered ineligible for the study.**

Rev. 1/16

Rev. 2/15  
Rev. 9/16

- \_\_\_\_\_ 3.2.3 Patient must be registered/randomized to Step 2 within a maximum of 7 weeks following surgery.
- \_\_\_\_\_ 3.2.4 Women of childbearing potential and sexually active males are strongly advised to use an accepted and effective method of contraception

\_\_\_\_\_  
Physician Signature

\_\_\_\_\_  
Date

**OPTIONAL:** This signature line is provided for use by institutions wishing to use the eligibility checklist as source documentation.

Rev. Add8

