## 9. Statistical Considerations

Rev. 2/15

This is a phase II trial of p16+ (using immunohistochemistry (IHC)) OPSCC patients that will undergo transoral surgery (TOS, Step 1) followed by risk-adjusted radiotherapy (Step 2). Patient risk status is determined after surgical excision and is defined in Section 5.1. Patients with low-risk will be assigned to the observation group (Arm A). Patients with intermediate-risk (the primary study group) will be equally randomized to receive radiotherapy IMRT 50 Gy (Arm B) or 60 Gy (Arm C), stratified by current/former smoking history ( $\leq 10$  vs.  $> 10$  pack-years). Patients with pathological N2C/N3 disease without extensive ECS (and do not meet the high risk feature) will be directly assigned to Arm C receiving IMRT 60 Gy. Patients with high-risk will receive concurrent cisplatin and IMRT 66 Gy (Arm D). Among the first 10 patients enrolled on Arm A, if 2 or more progress or die within 1 year, currently enrolled and subsequently enrolled patients with low risk who have not progressed will be directly assigned to radiotherapy 50 Gy (details are given below).

The study requires 180 evaluable patients with intermediate risk (to be randomized between Arms B/C). Based on results from the interim analysis prepared for the Fall 2015 DSMC meeting, the overall proportion of evaluable patients with intermediate risk is estimated to be 35% (~73% patients are evaluable, among whom ~48% are intermediate risk), which is lower than the originally estimated 48% (80% evaluable, among whom 60% would be intermediate risk). Here, patients who are eligible and started treatment on step 2 are considered as evaluable. As stated in the original design, if the observed proportion of patients with intermediate risk is off over 5% from the anticipated 60%, accrual goal would be adjusted. Therefore, the current section incorporates a sample size increase from the originally proposed 377 to 515 ( $180/0.35=515$ ), to ensure 180 evaluable patients with intermediate risk to be randomized. Based on the observed accrual rate of 18.5 patients per month, this new accrual goal can be achieved in February, 2017.

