## 9.2 Sample Size and Accrual Rate

We plan to accrue 515 patients, expecting ~376 (73%) total patients would be evaluable (eligible and treated on step 2), among whom 180 would be intermediate risk. Observed accrual rate (18.5 patients per month) is higher than the original assumption of 8 patients per month, so accrual of 515 patients is expected to complete in February, 2017.

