In the original design, the risk distribution was assumed to be 10% low risk, 60% intermediate risk, and 30% high risk, and an interim analysis for the first 59 patients who complete transoral resection was scheduled. Based on the analysis results, among the 104 evaluable patients (not ineligible based on current evaluation, and started treatment on step 2), the estimated risk distribution is: 8% low risk, 48% intermediate risk and 32% high risk (13 (12%) patients had potentially misclassified risk category/ arm based on their surgical data and the study team is taking various actions trying to improve this). As was stated in the original design, in case the proportion of the intermediate risk patients is off over 5% from the anticipated 60%, the accrual goal would be adjusted, With this new accrual goal, we expect at the end of the study ~180 evaluable patients would be intermediate risk, ~120 high risk, and ~30 low risk.

In analyzing the 2-year PFS rate, 90% exact binomial confidence intervals will be computed for each arm. Only eligible patients with confirmed P16+ status who started radiotherapy will be analyzed (by arm). The regimen will be considered worthy of further study if the higher limit of the computed 90% CI exceeds 85%.

Comparisons of 2-year PFS rates between Arms B and C, Arms B and D, and Arms C and D are exploratory endpoints. Since one of the randomized arms proposed in this study is likely to be selected for a follow-up phase III study, the exploratory comparison of 2-year PFS rate between the two randomized arms is more important and a p-value  $\leq 0.05$  will be considered statistically significant. For the other two comparisons (Arms B and D; Arms C and D), the Type I error rate of 5% will be divided by the two tests (i.e., 0.05/2 considered statistically significant). Therefore, the family-wise error rate of 0.10 will be protected for the multiple comparisons in the 2-year PFS rate among arms. Power for various differences in the 2-year PFS rate is shown below, assuming a two-sided Fisher's exact test and 90 analyzable patients in Arms B or C, and 120 analyzable patients in arm D.

Difference in 2-year PFS rate between arms	Arm C vs. Arm B	Arm B (or C) vs. Arm D
10% (85% vs. 75%)	0.32	0.27
15% (85% vs. 70%)	0.62	0.58
20% (85% vs. 65%)	0.85	0.83
25% (85% vs. 60%)	0.96	0.96

*Interim Analysis—1-year PFS rate*

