To safeguard against an unacceptably high failure rate for Arm B and Arm C, in which both the radiation dose is reduced and chemotherapy is removed, an interim look at 1-year PFS rate will be performed for the first 40 eligible and treated patients in Arm B and Arm C, separately. It is expected, for either arm, 90% of patients will be alive and progression free at 1 year (Fakhry, C, JNCI, 2008). The event rate will be deemed too high if 6 or more such events are observed within 1 year, which corresponds to an empirical progression rate of 15%. In this case, the trial will be suspended and a panel review will be called. The following table summarizes the probability of suspending the trial under various true 1-year progression rates in Arm B (and Arm C). For instance, the probability of suspending the trial is at least 84% if the true 1-year progression rate is 20% or higher. The study will continue accrual while we are waiting for the decision from this interim analysis.

True 1-yr progression rate for patients with intermediate risk	0.10	0.15	0.20	0.25	0.30
Probability of suspending the trial	0.21	0.57	0.84	0.96	0.99

Similarly, to safeguard against an unacceptably high failure rate for the observational Arm A, an interim look at 1-year PFS rate will also be performed for the first 10 eligible and treated patients (a total of 38 patients is expected to be accrued to this arm). Among these 10 patients, if 2 or more patients progressed or died within 1 year, currently enrolled and subsequently enrolled low risk patients who have not progressed will be directly assigned to radiotherapy IMRT 50 Gy. The same interim monitoring rule will be applied to the patients with pathological N2C/N3 disease who are directly assigned to Arm C (expected to be 5% of the total population). That is, if 2 or more patients among the first 10 such patients progress or die within the first year, currently and subsequently enrolled patients with p N2C/N3 disease will be treated with IMRT 66 Gy + cisplatin (Arm D treatment). The following table summarizes the probability of observing 2 or more events, under various true 1-year PFS rate for this group of patients.

True 1-yr PFS rate	0.10	0.15	0.20	0.25	0.30
Probability of observing 2 or more events	0.26	0.46	0.62	0.76	0.85

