### *Risk Distribution*

Given the distribution of the histologic risk is unknown, this trial provides an opportunity to find out patient distribution in each risk cohort. A 90% binomial confidence interval will be estimated for the percentage of patients in each risk group. All eligible patients on Step 2 will be analyzed. It was expected 60% patients would be intermediate risk in the original design.

An interim analysis was planned in the original design: among the first 59 patients who have completed transoral resection and have risk status evaluated, if 21 (36%) or fewer are intermediate risk, the percentage will be deemed too low. Based on results from the interim analysis, the estimated proportion for the intermediate risk category is 48%, among the 104 evaluable patients.

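### Sections 3.2.2 and 9.4 together delete confirmed misclassified patients from the risk-distribution endpoint, while the interim 48% kept 13 potentially misclassified patients in the denominator and in no class

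*Combined protocol and SAP*

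**What the plan says.** Section 3.2.2 lists the risk classes and ends with this rule: "Patients not categorized into the appropriate risk category will be considered ineligible for the study". The opening of Section 9 defines the analysis population: "patients who are eligible and started treatment on step 2 are considered as evaluable". Section 9.4 (Risk Distribution) promises a 90% binomial confidence interval for the percentage in each risk group and fixes the set: "All eligible patients on Step 2 will be analyzed".

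The interim estimate in Section 9.3 is taken "among the 104 evaluable patients (not ineligible based on current evaluation, and started treatment on step 2"). It gives 8% low, 48% intermediate and 32% high risk, and adds that "13 (12%) patients had potentially misclassified risk category/ arm based on their surgical data" and that the study team is acting to improve this. Section 9.4 repeats the 48% of 104 as the interim result.

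Section 9.2 carries the 73% evaluable rate forward, "expecting ~376 (73%) total patients would be evaluable (eligible and treated on step 2"). Section 9.3 expects about "180 evaluable patients would be intermediate risk, ~120 high risk, and ~30 low risk". Sections 3.2.2 and 4.2.4.1 also define an unknown-risk class, pN2c/N3, which Section 9.3 says is "expected to be 5% of the total population".

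**The concern.** Section 9.1 names the patient risk distribution, and the intermediate share in particular, as a measure of feasibility. The plan does not say how a patient found to be in the wrong class enters that distribution.

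Read together, Sections 3.2.2 and 9.4 remove such a patient once the error is confirmed. That selection rule is tied to the quantity being estimated: a patient is dropped because of a mistake about the very class that is being counted, although the surgical data that expose the mistake can also show the right class. The interim tabulation did something else and left these patients in the total without a class. Neither treatment gives the distribution of pathologic risk in the patients studied.

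The strategy under test assigns adjuvant therapy by pathologic risk. The frequency of wrong assignment is therefore a feasibility result in its own right, yet the three feasibility endpoints in Section 9.4 give it no place. Section 1.3 says the trial's data are to guide the design of a later phase III trial.

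**Working it through.** **Inputs.** Sections 9 and 9.2: accrual goal 515, 73% evaluable, 376 evaluable, 180 intermediate required. Section 9.3: 104 evaluable at the interim; 8%, 48% and 32%; 13 potentially misclassified; expected class totals 180, 120 and 30.

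**Step 1: reproduce the plan's figures.** 515 × 0.73 = 375.95, stated as 376. 0.73 × 0.48 = 0.350, and 180/0.35 = 514.3, rounded up to 515. Both agree.

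**Step 2: recover the interim counts.** The only whole numbers out of 104 that round to 8%, 48% and 32% are 8, 50 and 33. They sum to 91, and 91 + 13 = 104 exactly. So the 13 are in the denominator and in none of the three numerators.

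**Step 3: intermediate share under each treatment of the 13** (exact Clopper-Pearson 90% intervals).

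| Treatment of the 13 | Share | 90% CI |
|---|---|---|
| Kept, in no class (as reported) | 50/104 = 48.1% | 39.7-56.6% |
| All confirmed and excluded | 50/91 = 54.9% | 45.8-63.9% |
| Reassigned, none truly intermediate | 50/104 = 48.1% | 39.7-56.6% |
| Reassigned, all truly intermediate | 63/104 = 60.6% | 52.1-68.6% |

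Against the anticipated 60%, with the 5-point tolerance in Section 9.3, these shares are 11.9 points below, 5.05 points below (only just outside) and 0.6 points above.

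**Step 4: direction of bias.** Exclusion equals the correctly reassigned share when (50 + x)/104 = 50/91, that is, x = 104 × 50/91 − 50 = 7.1, where x is the number of the 13 who are truly intermediate. With 7 or fewer, exclusion overstates the share; with 8 or more, it understates it. The documents do not give x.

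**Step 5: partial confirmation.** If k of the 13 are confirmed and excluded, the share is 50/(104 − k), and the evaluable total is 515 × 0.73 × (104 − k)/104.

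| k | Share | Evaluable of 515 |
|---|---|---|
| 0 | 48.1% | 376 |
| 3 | 49.5% | 365 |
| 7 | 51.5% | 351 |
| 10 | 53.2% | 340 |
| 13 | 54.9% | 329 |

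**Step 6: expected totals.** 180 + 120 + 30 = 330, and 376 − 330 = 46, which is 12% of 376. The three totals are 0.48 × 376 = 180, 0.32 × 376 = 120 and 0.08 × 376 = 30, so all rest on the denominator of 376. At full size the share is 180/376 = 48% (44-52%) if the 46 stay unclassified, and 180/330 = 55% (50-59%) if all are excluded.

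**Step 7: targets.** With all 13 excluded, the evaluable rate is 0.73 × 91/104 = 0.639, and 0.639 × 50/91 = 0.351. This is the same 35% overall yield, so 180 and 515 stand.

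**Step 8: pN2c/N3.** Since 8 + 50 + 33 + 13 = 104, the unknown-risk class has no share of its own. It was either absent or folded into another row; the text does not say which.

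**The case against.** The strongest reply is that the interim was provisional. Section 9.3 calls the 13 only potentially misclassified and describes the 104 as not ineligible on current evaluation. Section 12.1 provides for a retrospective pathology review to settle evaluability. Counting patients not yet found ineligible does not breach Section 3.2.2. January 2016 revision marks stand beside that section, while the interim was prepared for Fall 2015, so the ineligibility sentence may even post-date the data cut; the text cannot settle this. All of this stands. It makes 55% and about 330 the end of a range, but it does not supply the rule for the final analysis.

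A reader might also draw four stronger conclusions that the documents do not support.

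- *That 376 and 330 come from two conflicting eligibility rules.* They do not: 180, 120 and 30 are 48%, 32% and 8% of the same 376. The gap shows only that about 12% have no class.
- *That deletion inflates the intermediate share.* Step 4 shows that the direction depends on true classes that are not given.
- *That the plan conceals the misclassification.* Section 9.3 reports it openly, with the response to it. What is missing is a place for it among the final feasibility results.
- *That the interim and final populations differ in stage.* The original plan looked at resected patients with risk evaluated, but the reported interim estimate used patients who had started Step 2, close to the final set. Restricting to Step 2 is defensible, because risk class is recorded at Step 2 registration.

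It is also fair to say that Section 9.4 attaches no final decision rule to the risk distribution, only an interval, and that no section says this share will size the phase III trial.

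**Conclusion.** The concern holds in this form. As written, the final analysis would delete confirmed misclassified patients from a primary feasibility endpoint, whereas the reported interim estimate left 13 of 104 in no class. The intermediate share is 48% as reported, up to 55% under full exclusion, and between 48% and 61% under correct reassignment. The 48% is the lowest of these values, because none of the 13 counts in its numerator. That statement assumes that the other 91 are correctly classed and that no pN2c/N3 patients sit within the 50.

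The evaluable total of about 376 (73%) would fall to as few as about 330 (64%) if every such patient were confirmed ineligible and the 12% rate persisted. The study team's corrective action may lower that rate. The 180 and 515 targets are unaffected, so the point bears on how a primary endpoint is estimated and reported and not on the size of the trial. It should be corrected before the final analysis.

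**What to change.** 1. **Section 9.4.** Count each eligible Step 2 patient once, in the class given by the reviewed surgical pathology. Keep misclassified patients in the risk-distribution set, give pN2c/N3 its own row, and report the number assigned to the wrong class or arm as a separate feasibility result.
2. **Section 3.2.2.** State that misclassification affects the per-arm efficacy set and not the risk-distribution set.
3. **Section 9.2.** Give the expected evaluable total as a range, about 330 to 376, depending on how many patients are confirmed misclassified.
4. **Optional.** Add a sensitivity tabulation that includes resected patients with final pathology who never reach Step 2.

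The cost is protocol and SAP wording plus one re-tabulation. Surgical and pathology reports are already mandatory submissions under Section 7.2, so no new data are needed. The lower end of the stated evaluable rate becomes less favourable, at 64% against 73%.

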#### 4. Registration and Randomization Procedures

##### CTEP Registration Procedures

Food and Drug Administration (FDA) regulations and National Cancer Institute (NCI) policy require all individuals contributing to NCI-sponsored trials to register and to renew their registration annually. To register, all individuals must obtain a Cancer Therapy Evaluation Program (CTEP) Identity and Access Management (IAM) account (<https://ctepcore.nci.nih.gov/iam>). In addition, persons with a registration type of Investigator (IVR), Non-Physician Investigator (NPIVR), or Associate Plus (AP) (i.e., clinical site staff requiring write access to OPEN, RAVE, or TRIAD or acting as a primary site contact) must complete their annual registration using CTEP's web-based Registration and Credential Repository (RCR) (<https://ctepcore.nci.nih.gov/rcr>). Documentation requirements per registration type are outlined in the table below.

Documentation Required	IVR	NPIVR	AP	A
FDA Form 1572	✓	✓		
Financial Disclosure Form	✓	✓	✓	
NCI Biosketch (education, training, employment, license, and certification)	✓	✓	✓	
HSP/GCP training	✓	✓	✓	
Agent Shipment Form (if applicable)	✓			
CV (optional)	✓	✓	✓	

An active CTEP-IAM user account and appropriate RCR registration is required to access all CTEP and CTSU (Cancer Trials Support Unit) websites and applications. In addition, IVRs and NPIVRs must list all clinical practice sites and IRBs covering their practice sites on the FDA Form 1572 in RCR to allow the following:

- Added to a site roster
- Assigned the treating, credit, consenting, or drug shipment (IVR only) tasks in OPEN
- Act as the site-protocol PI on the IRB approval
- Assigned the Clinical Investigator (CI) role on the Delegation of Tasks Log (DTL).

Additional information can be found on the CTEP website at <https://ctep.cancer.gov/investigatorResources/default.htm>. For questions, please contact the RCR **Help Desk** by email at [[contact]](mailto:[contact]).

##### CTSU Registration Procedures

This study is supported by the NCI Cancer Trials Support Unit (CTSU).

Each investigator or group of investigators at a clinical site must obtain IRB approval for this protocol and submit IRB approval and supporting documentation to the CTSU Regulatory Office before they can be approved to enroll patients. Assignment of site registration status in the CTSU Regulatory Support System (RSS) uses extensive data to make a determination of whether a site has fulfilled all regulatory criteria including but not limited to the following:

- An active Federal Wide Assurance (FWA) number
- An active roster affiliation with the Lead Network or a participating organization

- A valid IRB approval
- Compliance with all protocol specific requirements

In addition, the site-protocol Principal Investigator (PI) must meet the following criteria:

- Active registration status
- The IRB number of the site IRB of record listed on their Form FDA 1572
- An active status on a participating roster at the registering site.

Requirements for E3311 site registration:

- IRB approval (local IRB documentation, an IRB-signed CTSU IRB Certification Form, Protocol of Human Subjects Assurance Identification/IRB Certification/Declaration of Exemption Form, or combination is accepted)

### **Downloading Site Registration Documents**

Site registration forms may be downloaded from the E3311 protocol page located on the CTSU members' website.

- Click on the Protocols tab in the upper left of your screen
- Either enter the protocol # in the search field at the top of the protocol tree, or
- Click on the By Lead Organization folder to expand
- Click on the ECOG-ACRIN link to expand, then select trial protocol #E3311
- Click on LPO Documents, select the Site Registration documents link, and download and complete the forms provided.

### **Required Protocol Specific Regulatory Documents**

1. **CTSU Regulatory Transmittal Form.**
2. **Copy of IRB Informed Consent Document.**

**NOTE:** Any deletion or substantive modification of information concerning risks or alternative procedures contained in the sample informed consent document must be justified in writing by the investigator and approved by the IRB.

3. **A. CTSU IRB Certification Form.**

**Or**

B. Signed HHS OMB No. 0990-0263 (replaces Form 310).

Or

C. IRB Approval Letter

4. Surgeon Certification Form (See Section [4.1.5.6](#)).

**NOTE:** The above submissions must include the following details:

- Indicate all sites approved for the protocol under an assurance number.
- OHRP assurance number of reviewing IRB
- Full protocol title and number
- Version Date
- Type of review (full board vs. expedited)
- Date of review.
- Signature of IRB official

Rev. 2/14,

